Data collection for all subjects will be conducted in the BioMotion Laboratory the CCTS and the MRISC at the University of Kentucky. Testing sessions may last approximately 6 hours depending on scheduling of the MRISC and CCTS procedure room. Subjects will be requested to wear sports clothes (e.g. athletic shoes, shorts, and t-shirt). The first data collection will occur before they start the treatment program and will consist of all study procedures except running and jumping. The second data collection will occur before surgery and will consist of measuring intake scales, quadriceps strength, and walking gait. Following surgery, subjects will be administered the intake questions at regular intervals to help the study staff assist them with attending their physical therapy visits. We will then administer all study interventions except running and jumping between 3-4 months after surgery. The last data collection will occur 6-7 months after surgery and will include quadriceps strength assessment, walking and running gait, step down test performance and jumping. The timing of testing maybe delayed by upto 1-2 weeks if the subject is out of town for vacation or illness.

Research procedures for the muscle biopsy and MRI arm of the study will follow procedures already within another study focused on subjects with an ACL tear and reconstruction (11-0388):

Patients will be asked to stop taking aspirin 5 days and NSAIDS 3 days prior to starting the study. Study personnel will confirm that they have not taken aspirin or NSAIDS prior to the start of the muscle biopsy. Those who do not will be excluded from the additional analysis.

Muscle Biopsy: A muscle biopsy sample will be obtained from the vastus lateralis of both thighs in individuals before surgery and again when they have been cleared to practicing drills for their sport or are in a maintenance phase of physical therapy. The muscle biopsy procedure will proceed as follows for each subject taking approximately 15 minutes.

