Continuous participant demographic variables (e.g., age, body mass index (BMI), time since surgery) were summarized with descriptive statistics (e.g., sample size, mean, standard error). Categorical variables (e.g., sex assigned at birth) were summarized with descriptive statistics (e.g., counts and percentages). Summary statistics are also presented by treatment group. A chi-squared test was used to evaluate between-group differences in sex assigned at birth and two-sample *t*-tests were used to evaluate between-group differences in quantitative covariates.

All primary and secondary outcomes were continuous. For each outcome, change scores were calculated as: post-intervention (4-5 months post-surgery) – pre-intervention (baseline pre-surgery). Two-sample *t*-tests were then used to assess between-group differences in change scores. Distributional assumptions of two-sample *t*-tests were assessed using plots of each outcome. An analysis of blinding was performed for each of the participants, the data analysts, and the primary investigator of the study. Chi-square tests (or Fisher's exact tests in the case of small cell counts) were used to identify any association between guesses and treatment group for each of the blinded groups. All analyses were performed using R (R version 4.1.2, R Core Team, 2023) and *p*-values ≤ 0.05 were considered statistically significant.

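### The post-operative muscle biopsy has three conflicting timings, one of them an undated recovery milestone, so the arms may be sampled at different times after surgery

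*Combined protocol and SAP*

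**What the plan says.** Four parts of the document bear on when the biopsies are taken.

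- **Muscle Biopsy paragraph (Data Collection & Research Materials).** The vastus lateralis is sampled in "both thighs in individuals before surgery and again when they have been cleared to practicing drills for their sport". An alternative trigger for the second sample is that therapy has reached a maintenance stage. Neither sample has a date or window in this paragraph.
- **Visit schedule (same section).** "The first data collection will occur before they start the treatment program and will consist of all study procedures except running and jumping". A separate pre-surgery visit follows: "The second data collection will occur before surgery and will consist of measuring intake scales, quadriceps strength, and walking gait". After surgery: "We will then administer all study interventions except running and jumping between 3-4 months after surgery". The last visit, at 6-7 months, lists strength, gait, step-down and jumping, but no biopsy.
- **Payment.** The biopsy is among the compensated items, and $100 of the $200 is paid after a visit at 4-5 months. The food record is also placed at 4-5 months.
- **Statistical Analysis.** The follow-up value in each change score is "post-intervention (4-5 months post-surgery", and the starting value is a pre-intervention, pre-surgery baseline. The arms are compared with two-sample t-tests on change scores. Time since surgery appears only as an example of a descriptive variable.

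Objective 3 concerns the effect of the bands on muscle fibre size and type and on stem and progenitor cells. It rests on these samples. Blood is also drawn at both biopsy times.

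**The concern.** Randomisation makes the arms comparable at entry. It does not keep them comparable if each participant is then measured at a moment that depends on how recovery has gone. Clearance for drills and entry to a maintenance stage are stages of rehabilitation, and the intervention is quadriceps training given during that rehabilitation. If training changes how soon a participant reaches either stage, time from surgery to the second biopsy becomes a post-randomisation variable that can differ by arm.

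Muscle after ACL reconstruction is not expected to be in a steady state, so a gap in sampling time between arms can by itself produce a difference in histology or conceal one. A reader of the Objective 3 result could not separate an effect of the bands from an effect of elapsed time. Serum collected at the same visits would carry the same problem.

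**Working it through.** The documents give no power calculation, effect size or SD, so there is no stated figure to reproduce. The check is a comparison of the timing statements, followed by an illustration on assumed values.

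**1. The second biopsy, side by side**

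| Source | Timing after surgery |
|---|---|
| Muscle Biopsy paragraph | Undated: drill clearance or maintenance stage |
| Visit schedule | 3-4 months |
| Statistical Analysis | 4-5 months |
| Payment | Refers to a 4-5 month visit |

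The two dated windows share only the 4-month boundary. Together they run from 3 to 5 months, a span of 5 − 3 = 2 months. The milestone has no bound at either end.

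**2. Do the general allowances reconcile them?** No. Testing may be delayed by 1-2 weeks for travel or illness, and the programme may be extended by 1-2 months for concurrent surgery or holidays. These widen the possible spread. They do not say which timing governs the biopsy.

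**3. Does the analysis deal with unequal timing?** The Statistical Analysis section has no covariate for time since surgery in the outcome comparison and no rule for samples outside 4-5 months. It does not name the histology outcomes. I assume that its change-score rule covers them, since it is stated for every primary and secondary outcome and no other comparative analysis is given.

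**4. The first biopsy, side by side.** The biopsy paragraph fixes it only relative to surgery. The schedule places all procedures except running and jumping before the treatment programme, and its list for the later pre-surgery visit contains no biopsy. The analysis labels the baseline as pre-intervention. Read together, the first biopsy is most naturally taken before any banded training.

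**5. Illustration of what a timing gap would do.** Let *b* be the between-arm difference in mean change score caused by timing alone, in SDs of the change score. The documents give no value for *b*, so the values below are assumed. Also assumed: no true effect, a 1:1 split, a two-sided test at 0.05 (sidedness is not stated), and a usable biopsy pair from everyone. With *n* = N/2 per arm, the noncentrality is *b* × √(n/2), and the rejection rate comes from the noncentral t distribution with N − 2 degrees of freedom.

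- N = 55 (cover form maximum): n = 27.5, √13.75 = 3.708. For *b* = 0.2 the noncentrality is 0.742.
- N = 60 (Study Population): n = 30, √15 = 3.873. For *b* = 0.2 the noncentrality is 0.775.

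| Assumed *b* (SD) | False-positive rate, N = 55 | False-positive rate, N = 60 |
|---|---|---|
| 0 | 5% | 5% |
| 0.1 | 6.5% | 6.7% |
| 0.2 | 11.3% | 11.9% |
| 0.3 | 19.4% | 20.8% |
| 0.5 | 44.5% | 47.8% |

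If timing is the same in both arms (*b* = 0), the nominal 5% is kept. The table is for a truly null effect. If there is a true effect, an artefact of opposite sign would mask it by the same amount.

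**The case against.** The best case for the plan is that the document, read as a whole, already places the second biopsy at a scheduled visit. The schedule puts all procedures at 3-4 months, the 6-7 month list has no biopsy, and the Payment section pays for a set of items that includes the biopsy. On this reading the milestone merely describes the stage a participant is expected to have reached by then. The maintenance-stage alternative also gives a route to sampling without drill clearance, and the document does not say how clearance is decided.

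Much of this is fair. It shows that the plan did not clearly choose a milestone over a visit; a reader might infer that it did, but the schedule contradicts that. It does not remove the conflict. The biopsy sentence is the most specific text on biopsies and gives no date, the alternative it adds is equally undated, and the two dated windows disagree.

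The 3-4 versus 4-5 month mismatch does affect every outcome measured at that visit. Specific to the biopsy is the third, recovery-dependent timing. It may also be said that time since surgery is listed as a variable and that quantitative covariates are compared between arms. That could reveal a gap, but the section does not tie the variable to the biopsy date, and the outcome test does not use it.

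Two stronger readings are tempting and are not supported:

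- **That the first biopsy misses the pre-operative training.** The biopsy paragraph taken alone would permit a sample after that training. The schedule and the pre-intervention label point the other way.
- **That the bias runs towards no difference.** This would require that the bands speed up clearance, that fibre measures are still improving with time, and that clearance tracks histology. The documents establish none of these.

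**Conclusion.** The concern holds for the second biopsy. Its timing is defined in three ways that do not agree, and following the biopsy sentence as written lets time since surgery differ by arm with no adjustment in the analysis. The Objective 3 comparison, and the serum drawn at the same times, could be biased in either direction. The size cannot be derived from the documents; the tabulated rates only show how sensitive a trial of 55 or 60 would be to an assumed artefact.

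The conclusion rests on two assumptions: that training could influence when the milestone is reached, and that the histology is analysed by the stated change-score rule. If in practice every second biopsy was taken in one common window whatever the arm, the contradiction is only in the wording, and reported dates would show that. For the first biopsy, a clarifying clause is all that is needed.

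**What to change.** 1. Reconcile the Muscle Biopsy paragraph, the visit schedule, the Payment section and the Statistical Analysis section to one post-surgery window for the second research biopsy. It should be the same in both arms and the same as the change-score window.
2. State how samples outside that window are handled in the analysis.
3. Report actual days from surgery to the second biopsy by arm, as a distribution and not only a mean.
4. Add a sensitivity analysis of the histology change scores adjusted for days since surgery. Keep it as a sensitivity analysis: days since surgery may itself be affected by treatment, so the adjusted estimate also needs cautious reading.
5. As a minor clarification, say in the biopsy paragraph that the first biopsy belongs to the first data collection, before the treatment programme, as the schedule already implies.

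The Study Population section ends enrolment on September 1, 2022, and the analysis is written in the past tense, so samples may already have been taken. Item 1 then becomes a statement of what was done. Items 2 to 4 remain possible, provided that the biopsy and surgery dates were kept. The cost is less flexibility in booking the procedure for any biopsies still to come, and slightly more analysis work.

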Muscle power testing: Subject will be in a seated position and a stabilizing strap will be placed around the thigh. A second strap will be placed around the bottom on the lower leg and attached to the isokinetic dynamometer. The subject will be assessed with the resistance set at one-third of the maximum strength. The subject will kick out up to 10 times against this resistance from which we will determine features of muscle power.

Subjects will be asked to rate their pain on a scale from 1-10 during a practice trial and during testing. If subjects rate their pain as a 3 or above, they will be given the option to use a pain reducing modality such as icing, taping, or e-stim. During their practice trial they will select which one they will use of the three. During the testing, the selected modality will be employed for the entirety of the strength testing protocol.

Assesment of hyperalgesia: A pressure algometer will be placed on the upper thigh of the subject and the pressure gradually increased until the point when the feeling of pressure first becomes that of pain. The subject will then press a trigger which will record that pressure value and end the test. The test will be repeated several times. These assessments will occur once before surgery and then during each physical therapy visit during the first two weeks of post operative care to determine the extent hyperalgesia in the acute phase after surgery.

Attachments

Data Collection & Research Materials

In this section, please provide the following:

- Describe all sources or methods for obtaining research materials about or from living individuals (such as specimens, records, surveys, interviews, participant observation, etc.), and explain why this information is needed to conduct the study.
- For each source or method described, please list or attach all data to be collected (such as genetic information, interview scripts, survey tools, data collection forms for existing data, etc.).
- If you will conduct a record or chart review, list the beginning and end dates of the records you will view.

Treatment program: The subjects will complete one of two programs. Both groups will receive the same training protocol with the only difference being one group will receive the use of the air bands that are inflated to a greater pressure. The use of the bands will follow

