manufactures guidelines for use and is FDA approved. The groups will be randomized into the either of the two groups, through a computer assignment. The first group will use air bands inflated to provide restriction (40-60% occlusion). The other group will have the bands placed on their leg but they will be inflated a minimal amount (approximately 5% occlusion). Subjects will be instructed to be well hydrated prior to starting the training session. We will provide water and Gatorade to subjects if requested. These subjects will wear the BFRT air bands on their thighs only during the portion of the training designed to target their quadriceps muscle.

Their protocol will focus on quadriceps strengthening, and will be progressed per typical ACL protocols with exercises such as knee extension exercises, lunges, step downs, step ups, single leg squats, straight leg raises, and mini squats and wall sits performed as appropriate depending on the stage of rehabilitation. Subjects will also complete standard pre-operative and following surgery post operative physical therapy as part of their treatment session without the bands in the lab until they complete the study. This may include ice over the knee, range of motion exercises, hip strength exercise, neuromuscular re-education exercise and gait training exercises as needed and the subject's impairments dictate. Additionally, the program maybe extended 1-2 months depending on other surgical procedures that may occur at the same time of surgery (ie meniscus repair) and/or subject vacation and holidays that may delay finishing the protocol.

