Describe why potential benefits are reasonable in relation to potential risks. If applicable, justify why risks to vulnerable subjects are reasonable to potential benefits.

Risks strength assessment and training are minimal and include muscle or joint soreness during and after the training session. The training program proposed has been shown to be safe within the population to be tested [2, 6]. Subjects will be closely monitored by the research team during data collections. The lab is only accessible with badge access and remains locked.

Muscle Biopsy. Potential risks involved within the study procedures include those during the muscle biopsy and exercise testing. With the muscle biopsy procedure, there is a risk of bleeding, bruising, pain, infection, and scarring of the skin. Bleeding could rarely result in development of a hematoma. Pain and soreness usually resolves within 24-48 hrs post-procedure. Numbness of the skin near the biopsy site may occur and is usually temporary, but this numbness may persist indefinitely. An allergic reaction to the anesthetic also may occur but is rarely seen.

Blood draws. There is a risk of local pain, soreness, bleeding, bruising and swelling, as well as lightheadedness, dizziness and rarely, fainting and/or a local infection.

MRI. The risks from MRI are minimal. The images taken will be of the quadriceps muscle and used to construct muscle fibers and determine muscle volume. They are used only for research and are not read for any clinical interpretation.

Possible Risk/Side Effect from MR Scanning How often has it occurred? How serious is it? Can it be corrected?

Claustrophobia It occasionally occurs Can be treated Yes, volunteer is removed from the magnet

Loud noise It is expected to occur Not serious Yes, participants wear ear protection

Subjects will not receive any direct benefit from participating in this study. Risks to the subjects are minimal as strength is the primary outcomes being measured. If patients choose to participate in the study, the benefit to general knowledge may be great.

Available Alternative Opportunities/Treatments

Describe alternative treatments or opportunities that might be available to those who choose not to participate in the study, and which offer the subject equal or greater advantages. If applicable, this should include a discussion of the current standard of care treatment(s).

There is no alternative treatment to this study other than not participating in the study.

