Moderate: Discomfort sufficient to reduce or affect normal daily activity.

Severe: Incapacitating with inability to work or perform normal daily activity.

Attribution scale for AE reporting:

Probable: AE is related to the procedure (muscle biopsy), including pain, bleeding, infection, and death, if death resulted from one of the aforementioned complications.

Possible: AE follows the biopsy within a reasonable period (within 7 days), but may have been produced by other factors.

Remote: AE does not follow the biopsy within a reasonable period (more than 7 days) and could readily have been produced by other factors.

Unrelated: AE is judged to be clearly due to extraneous causes and does not meet the above criteria.

Monitoring Plan: Monitoring for adverse events will be conducted in real-time by the principal investigators and study coordinators.

Risks involved with this study are considered greater than minimal risk. For this reason, we will utilize the standing independent Data Safety Monitoring Board (DSMB) as chartered by the University of Kentucky Center for Clinical and translational Science (CCTS) to monitor the safety of this study. None of these individuals have any conflicts with this project, and therefore can serve the role of an impartial board who have expertise with these studies but who can oversee safety without bias. The DSMB will meet semiannually or as needed, and will review subject recruitment, AE's, side effects, laboratory results, withdrawals, protocol violations, and inclusion/exclusion criteria. More frequent meetings will take place if necessary or if side effects or other problems are prevalent.

AE Reporting Serious: AEs will be reported verbally to the IRB and CCTS OUTPATIENT UNIT within 24 hours and in writing within 48 hours of the event. Unanticipated events will be reported to the CCTS OUTPATIENT UNIT in real time and to the IRB no later than 48 hours after the event. Annual reporting of adverse events will be conducted with the IRB annual review/renewal according to their protocol. These reports will also be forwarded to the CCTS OUTPATIENT UNIT. The CCTS OUTPATIENT UNIT Administration will be informed within 15 days if for any reason the IRB or any other body temporarily or permanently suspends the study.

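### The adverse event attribution scale is tied to the muscle biopsy and cannot record relatedness to the randomised band pressure or the training; separately, the stated risk level differs between sections

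*Combined protocol and SAP*

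**What the plan says.** **Attribution.** Data and Safety Monitoring gives one four-grade scale:

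- The first grade rests on a causal link to the biopsy: "Probable: AE is related to the procedure (muscle biopsy), including pain, bleeding, infection, and death" (a fatal outcome counts when such a complication led to it).
- The second grade is set by a short interval since sampling: "Possible: AE follows the biopsy within a reasonable period (within 7 days), but may have been produced by other factors".
- The third grade is the late counterpart of the second: "Remote: AE does not follow the biopsy within a reasonable period (more than 7 days) and could readily have been produced by other factors".
- The last grade works by exclusion: "Unrelated: AE is judged to be clearly due to extraneous causes and does not meet the above criteria".

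**Intervention.** The treatment program, under Data Collection & Research Materials, gives both groups the same training, "the only difference being one group will receive the use of the air bands that are inflated to a greater pressure". The occlusion levels are 40-60% in one group and about 5% in the other.

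**Anticipated harm.** Potential Risks & Benefits names a harm of training: "Risks strength assessment and training are minimal and include muscle or joint soreness during and after the training session".

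**Who monitors.** "Monitoring for adverse events will be conducted in real-time by the principal investigators and study coordinators". Serious AEs go to the IRB verbally within 24 hours and in writing within 48 hours. The DSMB reviews AEs and side effects generally.

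**Analysis.** The Statistical Analysis section covers demographics, continuous outcomes and an analysis of blinding. It mentions no AE summary.

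**Risk level.** The risk assessment paragraph in Data and Safety Monitoring appears twice and each time calls the study minimal risk. The monitoring plan in the same section places the study above minimal risk and gives that as the reason for using the DSMB. Section 1 of the children's part records a level not above minimal, with a reason that concerns only the band.

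**The concern.** An attribution scale in a randomised trial should let the assessor say whether an event is related to what was randomised. Here it asks only whether the event is related to a tissue-sampling procedure that no section assigns by randomised group. If the scale is followed as written, the record cannot show that an event was judged related to the band or the training. That judgement bears on the statement in the children's part that adding the band carries no extra AE risk.

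The conflict over risk level matters for a different reason. The children's part of the form ties parental permission to the level chosen, and 10-15 participants under 18 are expected.

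**Working it through.** The plan states no figure on this point, so the check is a reading of the definitions side by side.

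**Step 1. What each grade can record.**

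| Grade | Defined by | Names the biopsy | Can record relatedness to band or training |
|---|---|---|---|
| Probable | relation to the biopsy | yes | no |
| Possible | 7 days or less after the biopsy | yes | no |
| Remote | more than 7 days after the biopsy | yes | no |
| Unrelated | extraneous cause and none of the above | only by reference back | no |

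Three of 4 grades name the biopsy, 1 of 4 works by exclusion, and 0 of 4 can record relatedness to the band or the training.

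**Step 2. Where an event caused by the band or training would go.**

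- *Within 7 days of a biopsy:* it can be graded Possible. The band then enters only as one of the other factors competing with the biopsy.
- *More than 7 days after a biopsy:* Probable fails because the biopsy is not the cause, and Possible fails on timing. Unrelated needs a clearly extraneous cause, and a study intervention is hard to call extraneous. Remote is the closest match on its literal terms, but it describes distance from the biopsy. No grade fits properly, and Remote is the likeliest code.

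Remote would therefore hold both events caused by the band and late events with no link to the study, and the grade could not separate them.

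**Step 3. Whether anything else compensates.** No second scale appears in the document. A table of AEs by arm would need no attribution, but the Statistical Analysis section does not describe one.

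**Step 4. Risk level, side by side.**

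| Place | Level | Remark |
|---|---|---|
| Children's part, Section 1 | not above minimal | reason covers the band only |
| Data and Safety Monitoring, risk assessment | minimal (twice) | direct statement |
| Data and Safety Monitoring, monitoring plan | above minimal | reason given for the DSMB |
| Potential Risks & Benefits | minimal | descriptive wording, not a formal level |

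The first two rows contradict the third. The reason given for children does not address the biopsy, the anaesthetic injection or the blood draws set out under Data Collection & Research Materials.

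**Step 5. Timing of any correction.** Planned enrolment ended September 1, 2022 and the document is dated 8/30/2024: 365 + 366 - 2 = 729 days. The Statistical Analysis section is already in the past tense, so any new attribution would be largely retrospective.

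**The case against.** The strongest reply is that no stated action turns on the grade. Serious and unanticipated events are reported without reference to it, the DSMB sees AEs and side effects in general, and no analysis uses it. All of that stands. A reader might infer that harms from the band would go undetected or unreported. The documents do not support that, and the point is limited to causality classification.

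Second, the attached data collection form was not available and may carry its own relatedness field. That also stands: the gap is shown for the written scale, not for what was recorded in practice. The written scale would still need correcting.

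Third, the other factors in Possible and Remote could include the band. They could, but only as an alternative explanation to the biopsy, never as a recorded relation to the intervention.

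Fourth, the Background describes adverse events with this training as exceedingly rare. Rarity lowers the expected count but does not give such an event a grade.

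On risk level, a reader might infer that permission for minors was inadequate. The form does ask for both parents, with exceptions, when risk is above minimal without direct benefit, and Potential Risks & Benefits says there is no direct benefit. One parent suffices for Categories 1 and 2. But the option ticked is not visible in the text. The study-specific entries in Section 2 of the children's part speak once of parents signing and once of the parent signing. Whether one or both sign is open, so no failure is shown.

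**Conclusion.** The point holds in two limited parts and should be fixed.

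1. As written, 0 of 4 attribution grades can record relatedness to the randomised band pressure or the training, and no described AE comparison by arm offsets this. The document gives no AE count, so no misclassification rate can be stated. It would be too strong to say that late events caused by the band are graded Unrelated; Remote is the likelier code. This rests on the scale being applied as written and on the unseen form holding no separate field.

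2. The monitoring plan's risk level contradicts the risk assessment in its own section and the children's part. Potential Risks & Benefits uses the word descriptively and should not be counted as a further formal contradiction. The expected 10-15 minors show who is concerned; they do not measure harm. The document does not settle which level is right.

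Neither part affects the comparison of the continuous outcomes.

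**What to change.** - **Attribution scale.** In Data and Safety Monitoring, attribute each AE separately to (a) the band or training and (b) research procedures, with a written definition for each. Have (a) judged by existing staff blinded to arm, such as the primary investigator, whom the Statistical Analysis section lists among the blinded. State whether the coordinators who also monitor AEs are blinded.
- **AE table.** Add to the Statistical Analysis section a table of all AEs by arm, regardless of attribution. This is the more dependable part, because re-attributing past events would rest on source notes that the document does not describe. Report that limit.
- **Risk level.** Reconcile the statements in the children's part and in the two paragraphs of Data and Safety Monitoring. Have the children's part address the biopsy, anaesthetic injection and blood draws as well as the band. Then check the parental-permission option against the reconciled level and state whether one or both parents sign.

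The cost is wording changes, an IRB modification and one extra table, with no new visits or participant data. The anticipated end date of 9/30/2025 is later than the document date, so the plan was still open to amendment at that date.
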